## **Risks to Subjects**

The potential risks to subjects for both groups include access site hematoma, pain, radial artery occlusion, and prolonged PACU recovery time. Potential transradial procedural related complications including pseudoaneurysm, digital ischemia, and arterial dissection are not inherently related to the timing of TR-Band deflation.

Per institutional protocol, the subjects will receive standard of care treatment as any similar patient in the same clinical scenario. Each planned procedure will involve a preprocedural evaluation including a sonogram of the radial artery that will be accessed during the procedure and Barbeau test conducted by the co-investigators under the supervision of the principal investigator. The Barbeau test will serve to rule out vascular compromise that may occur in the absence of sufficient vascular pressure. Not subject will be discharged until this is confirmed. Pre- and post-procedural laboratory values, including platelet count, activated clotting time and coagulation profile, will also be reviewed and analyzed. Following each procedure,

the subjects will be monitored for any immediate adverse events per the standard of care. As stated above, following discharge, the patient will be provided instructions as well as the contact information of the Nurse Coordinator for routine scheduling and care issues. In the case of an emergency, a Vascular and Interventional Radiology team of physicians and staff are on call 24 hours to manage any acute or emergent patient issues. All adverse events will be monitored, resolved, and recorded in the patient's medical record. Each case will be reviewed by PI or Co-I and IRB approved study staff to evaluate unanticipated problems or adverse events. These will be reported to IRB within 10 business days. An experienced VIR nurse, [name] will serve as an independent evaluator of each case to determine if unanticipated problem and adverse event might warrant the cessation of the study. The independent evaluator is not part of the IRB approved study team and will not be part of the publication of the findings. She will remain blinded to the unique study ID and will only have access to standard of care procedures and non-study data.

There is also a risk of loss of confidentiality. Being randomized to the expedited deflation group may be an additional risk.

#### Sharing of Results with Subjects

Individual test results, diagnostic tests and incidental findings will not be shared with subjects or others (e.g. the subject's primary care physicians).

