### **Study Endpoints**

The study participants will be randomly assigned into one of two groups; these groups will be defined based on the time from inflation to initiation of deflation of the TR-Band, i.e. the time to wean.

Group A (Total time about 60 minutes)	Group B (Total time about 120 minutes)
TR-Band Placed following your procedure	TR-Band Placed following your procedure
After 15 minutes deflated by 1/4	After 60 minutes deflated by 1/4
After 25 minutes deflated by 1/2	After 75 minutes deflated by 1/2
After 35 minutes deflated by 3/4	After 90 minutes deflated by 3/4
After 45 minutes deflated completely	After 105 minutes deflated completely
Observe your wrist for 15 minutes	Observe your wrist for 15 minutes
Remove TR-Band after 60 minutes	Remove TR-Band after 120 minutes

The primary outcomes will be the incidence of significant hematomas (> 5 cm in size), bleeding (continued ooze requiring re-inflation of the TR-Band or subcutaneous ecchymosis without a discernable hematoma) and occlusion of the left radial artery (based on ultrasound) at the procedure visit and at one month follow up visit

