After 35 minutes deflated by 3/4	After 90 minutes deflated by 3/4
After 45 minutes deflated completely	After 105 minutes deflated completely
Observe your wrist for 15 minutes	Observe your wrist for 15 minutes
Remove TR-Band after 60 minutes	Remove TR-Band after 120 minutes

If bleeding were to occur, the TR-Band will be re-inflated to the previous volume and the weaning protocol will be restarted after 15 minutes. Once the TR-Band is removed the patient will be re-evaluated for complications including hematoma, ecchymosis and occlusion.

Post-procedure, patients will return to the clinic 1 month following their procedure and be re-evaluated for radial access complications including hematoma, ecchymosis and occlusion; and for re-evaluation of the Barbeau test, and ultrasound.

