## **Data Management**

The data from living human subjects will include the physical examination, laboratory, and ultrasound data collected both immediately before and after the procedure; these include the pre-procedure History and Physical note, the procedure report, nursing notes and clinic Progress notes.

Only IRB approved team members will have access to the records of the patient's involved, which should be effective in controlling the confidentiality of the study. Individual, unique patient codes will be utilized in an Excel data spreadsheet for anonymization and subsequent analysis. These patient codes will be stored in a separate, secure location at the VIR Research Coordinator Office. The patient's safety will be ensured by the following methods. Prior to discharge from the PACU the patients will be given the contact information of the VIR Nurse Coordinator and clinic for any concerns. In addition, in the case of emergency, a VIR team of physicians and staff are on call at all times (24/7) to manage any acute or emergent patient issues.

The patients' characteristics (e.g. demographic information) will be compared using a t-test or chi-squared tests. The primary outcomes, i.e. rates of complications will be compared using a McNemar's test. An odds ratio will be estimated and its 95% confidence interval reported. Associations between preoperative factors and complications will be evaluated using logistic regression with random effects to account for multiple observations per patient.

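### The rule against sharing individual results has no exception for access-site complications, so read literally it covers a detected radial artery occlusion

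*Combined protocol and SAP*

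**What the plan says.** The section Sharing of Results with Subjects is a single sentence: "Individual test results, diagnostic tests and incidental findings will not be shared with subjects or others", followed by primary care physicians as an example. It is not limited to research-only data and carves out no complications.

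Study Endpoints makes "occlusion of the left radial artery (based on ultrasound) at the procedure visit and at one month follow up visit" part of the primary outcome. Study Design/Methods sets the same two occasions. On the procedure day, "Once the TR-Band is removed the patient will be re-evaluated for complications including hematoma, ecchymosis and occlusion". At one month patients return to clinic, are checked again for the same complications, and come "for re-evaluation of the Barbeau test, and ultrasound". Data Management counts as study data the "ultrasound data collected both immediately before and after the procedure", and names nursing and clinic notes among the sources.

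On the clinical side, Risks to Subjects says "the subjects will receive standard of care treatment as any similar patient in the same clinical scenario" and "All adverse events will be monitored, resolved, and recorded in the patient's medical record". Data Management adds that before discharge "patients will be given the contact information of the VIR Nurse Coordinator and clinic for any concerns", and both sections mention an on-call team.

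**The concern.** Radial occlusion is found by a diagnostic test, and the sharing rule says diagnostic tests are not shared with the subject. The Background says radial thrombosis rarely causes symptoms, so most affected patients would learn of it only by being told. Risks to Subjects lists occlusion as a risk in both groups and says that assignment to expedited deflation may itself add risk. If staff followed the sharing rule to the letter, a patient could have a study-related complication that the team had seen and recorded, and neither the patient nor the primary care physician would be told.

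**Working it through.** The check is a reading of one section against the others. The conclusion rests on no calculation.

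1. **Does the rule reach occlusion?** Yes. It names test results and diagnostic tests. Occlusion is determined by ultrasound (Study Endpoints), and the Barbeau test is repeated at one month (Study Design/Methods).
2. **Does the section limit itself?** No. It has no exception and no restriction to data held apart from clinical care. Data Management draws the study data from the clinical notes, so there is no separate research dataset to which the rule could be confined.
3. **Does another section override it?** No. Risks to Subjects covers treatment, monitoring, resolution and charting of adverse events. It does not mention telling the patient, and it is not framed as an exception to the sharing rule.
4. **What contact does the patient have after discharge?** There are three routes. The nurse coordinator's number and the on-call team depend on the patient noticing a problem. The one-month clinic visit does not, because it is scheduled for everyone. No step at that visit is described as giving the patient the findings.
5. **Does the rule differ by arm?** No. It applies alike to Groups A and B.

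For context only, this is how many occlusions the rule might apply to. The Background cites 6% asymptomatic occlusion in a first series of 100 transradial coronary angiograms; using that rate here is an assumption. Enrolment is up to 30, and 20 is an assumed lower figure. With n patients and rate p, the expected count is n × p and the chance of at least one is 1 − (1 − p)^n.

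- n = 30, p = 0.06: 30 × 0.06 = 1.8 expected; 1 − 0.94^30 = 0.844.
- n = 20, p = 0.06: 20 × 0.06 = 1.2 expected; 1 − 0.94^20 = 0.710.
- Assumed range p = 0.01 to 0.10: 0.3 to 3.0 expected (chance of at least one 0.260 to 0.958) with 30 patients; 0.2 to 2.0 (0.182 to 0.878) with 20.

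These figures count occlusions, not failures to disclose, so they carry no weight in judging severity.

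**The case against.** The best defence is that the rule was meant only for the return of research results. Read at its widest, it would also bar telling a patient about a type D Barbeau test, an out-of-range INR or a positive pregnancy test, all of which are part of screening, and that can hardly be intended. This makes a narrower intention plausible. The section does not express one, however, and a rule that overreaches this far needs a qualification.

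Second, adverse events belong to Risks to Subjects, where the investigators review each case and the event is resolved and charted. A complication treated under standard care would ordinarily become known to the patient. This stands as a reason to think non-disclosure is unlikely. A reader might go the other way and infer that the two sections contradict each other. They do not: Risks to Subjects is silent on telling the patient, so there is a tension that staff must resolve for themselves, not a direct conflict.

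Third, a reader might infer that a patient with a silent occlusion has no further contact unless symptoms appear. The one-month visit shows otherwise.

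Fourth, a reader might infer that an untold occlusion means a missed treatment. The documents name no treatment for an asymptomatic occlusion. The Background notes that the hand's double blood supply limits the harm of arterial damage, and Barbeau type D patients are excluded. What remains is the ethical case: a person who develops a listed complication of study participation should be told.

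Finally, the consent pages were removed before review and may contain disclosure wording. The point therefore concerns the protocol section as written.

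**Conclusion.** The point holds as a minor patient-safety and ethics wording defect. The sharing rule is an affirmative prohibition without exception. Its words cover the results that detect radial occlusion, and nothing in the supplied text overrides it. Standard care, charting and the one-month visit lower the practical risk but do not remove the instruction.

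The size is limited. The comparison between arms is unaffected, because the rule is the same in both. A reader might infer that patients will in fact go untold, or take the 84% above as the chance of that. Neither is supported: the documents say nothing about how staff would apply the rule, and the figure is only the chance that at least one occlusion occurs under a borrowed rate. The conclusion rests on the literal wording of the section and on the absence of an exception in the text available; consent wording could soften it.

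**What to change.** Add one sentence to Sharing of Results with Subjects:

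> Exception: a radial artery occlusion or other access-site complication found at the procedure visit or at one month will be told to the subject and, with the subject's agreement, to the primary care physician.

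The argument rests mainly on occlusion, because a hematoma larger than 5 cm at the wrist would ordinarily be apparent to the patient. Covering access-site complications together spares staff from deciding case by case. If the consent form repeats the sharing rule, it should carry the same exception.

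The cost is one sentence. Both assessments are already scheduled, so no test, discharge condition or recovery time is added. No attendance analysis is needed: the idea that telling patients would change who returns at one month is speculative.

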#### **Potential Benefits to Subjects or Others**

The potential benefits to the patients include a shorter PACU recovery times, less postoperative discomfort related to the insufflated TR-Band, and lower cost. The preoperative physical, laboratory and ultrasound examination will also help to clarify patient criteria for indications and contraindications for Expedited TR Band deflation by identifying demographic and anatomic risk factors for complications.

#### **Drugs or Devices**

There are no drugs or devices that will be used for this study that are outside what is used for the standard of care.

